6.5.2 Additional Follow-up Visits for All Subjects

Additional subject visits, such as unscheduled visits (other than the protocol required visits), may occur as clinically warranted. The following information will be collected and recorded in eCRF:

- Any adverse events
- Use and compliance of protocol required antiplatelet medication
- Details of any subsequent coronary interventions (e.g., repeat PCI or CABG)

If an unscheduled visit is conducted due to a suspected ischemic cardiac event, cardiac biomarkers and ECG may be performed per site's standard care.

All efforts must be made to obtain follow-up information on subjects who have undergone procedures or have been treated for adverse events in a non-trial-related hospital(s).

6.5.3 Unscheduled Angiography

There is no required angiographic follow-up for this clinical investigation. However, angiograms for all unscheduled revascularizations must be sent to the Angiographic Core Lab regardless of whether they are target or non-target vessel revascularizations. For all revascularizations performed on both the target lesion (TLR) and the non-target lesion of the target vessel (non-TLR), the angiographic core laboratory will determine the type of revascularization (i.e., TLR, TVR or non-TVR), stent thrombosis, or necessary assessments.

Clinical Investigation Plan

6.5.4 Schedule of Events

PROCEDURE/TEST	Baseline	Pre-Procedure (within 24 hours)	Procedure	Post-Procedure	1-month (30±7d) Office visit or phone contact ¹	6-month (180 ±14d) Office visit or phone contact ¹	12-month (365 ± 28d) Office visit or phone contact ²	24-month (730 ± 28d) Office visit or phone contact ¹	Unscheduled visits
Subject Medical/Clinical History (Age, Sex, Risk Factors, Cardiac Status, Cardiac History, Medical history)	✓								
Subject Informed Consent (Must be obtained prior to any trial related testing or procedures)	✓								
General Inclusion/Exclusion Criteria	✓								
ECG	✓			✓ ³					
Pregnancy test (for all female subjects of childbearing potential only)	✓								
Latest LVEF status ⁴	✓								
Angiographic Inclusion/Exclusion Criteria			✓						
Coronary Angiogram			✓						✓
Cardiac biomarker (CK-MB and Troponin) measurement(s)		✓ ⁵		✓ ⁶					
Stent and Procedure Information			✓						
Antiplatelet Medications Loading Dose		✓ ⁷	✓ ⁷	✓ ⁷					
Post-procedure Antiplatelet Medications				✓	✓	✓	✓	✓	✓
Adverse Events			✓	✓	✓	✓	✓	✓	✓

¹ Office visit is strongly recommended whenever possible.

² A formal office visit is required at 12-month follow-up to ensure a thorough clinical evaluation. A telephone contact is an option *only* for subjects who would otherwise be lost to follow-up due to being unable to complete an office visit.

³ If post-procedure ECG changes were observed signaling a peri-procedure MI, at least two cardiac biomarker tests are mandatory following the required post-procedure cardiac biomarker collection time window, even when the first CK-MB test is less than 1x URL.

⁴ LVEF within the past 3 months prior to the index procedure (has to be documented by any method)

⁵ Cardiac biomarker tests measuring creatine CK-MB and troponin must be conducted. If a ST-Elevation MI (STEMI) or non-ST-Elevation MI (NSTEMI) is identified based on a cardiac biomarker level, the cardiac biomarker level has to return to normal limits prior to index procedure in order for the subject to be registered in the clinical investigation. If the subject has stable coronary artery disease or silent ischemia, the pre-procedure cardiac biomarker can be obtained during procedure from the arterial sheath but prior to any angioplasty.

⁶ At post-procedure, at least one CK-MB test and at least one troponin test at post-procedure are mandatory for this clinical investigation:

- The first cardiac biomarker test must to be done between 6-10 hours post-procedure.
- If the first creatine kinase MB (CK-MB) test is equal or greater than 1x upper reference limits (URL) per site's standard of care (SOC), then a second cardiac biomarker test for both CK-MB and Troponin must to be done between 12-18 hours post-procedure, or prior to discharge.
- If the first CK-MB test is < 1x URL, then a second test is not required for both CK-MB and Troponin.
- Serial cardiac biomarker tests with 6-8 hours interval are strongly recommended until discharge only when CK-MB ≥ 1x URL.

Clinical Investigation Plan

⁷ It is recommended that the antiplatelet medication loading dose be given before the procedure (within 24 hours prior to procedure), at time of procedure, or post-procedure (recommended to be within 1-hour post-procedure).

7.0 ADVERSE EVENTS

To comply with worldwide standards and guidelines on clinical investigation adverse event reporting, the Sponsor has adopted uniform and worldwide applicable standard definitions and reporting timelines to be used and adhered to by the investigators.

7.1 Definition

7.1.1 Adverse Event

An adverse event (AE) is any untoward medical occurrence, unintended disease or injury, or untoward clinical signs (including abnormal laboratory findings) in subjects, users or other persons, whether or not related to the medical device under investigation.

Note 1: This definition includes events related to the medical device under investigation or the comparator.

Note 2: This definition includes events related to the procedures involved.

Note 3: For users or other persons, this definition is restricted to events related to medical devices under investigation.

7.1.2 Serious Adverse Event

If the AE meets any of the criteria below, it is regarded as a serious adverse event (SAE).

- a) Led to a death
- b) Led to a serious deterioration in health of the subject, that either resulted in
 1. a life-threatening illness or injury, or
 2. a permanent impairment of a body structure or a body function, or
 3. in-patient hospitalization or prolongation of existing hospitalization, or
 4. medical or surgical intervention to prevent life threatening illness or injury or permanent impairment to a body structure or a body function.
 5. chronic disease
- c) Led to fetal distress, fetal death or a congenital abnormality or birth defect

Note: A planned hospitalization for pre-existing condition, or a procedure required by the CIP, without a serious deterioration in health, is not considered to be an SAE.

Clinical Investigation Plan

7.1.3 Device Deficiency/Device Malfunction (if applicable)

Device deficiency is defined as an inadequacy of a medical device related to its identity, quality, durability, reliability, safety or performance, such as malfunction, misuse or use error and inadequate labeling. This includes the failure of the device to meet its performance specifications or otherwise perform as intended. Note: Performance specifications include all claims made in the labeling of the device.

A device malfunction is the failure of a device to meet its performance specifications or otherwise perform as intended, when used in accordance with the instructions for use or CIP.

7.2 Device Relationship

Determination of whether there is a reasonable possibility that an investigational product or device under investigation caused or contributed to an AE is to be **determined by the Investigator** and recorded on the appropriate CRF form. Determination should be based on assessment of temporal relationships, evidence of alternative etiology, medical/biologic plausibility, and subject condition (pre-existing condition).

7.2.1 Unanticipated (Serious) Adverse Device Effect [U(S)ADE]

Unanticipated serious adverse device effect (USADE) refers to any serious adverse effect on health or safety or any life-threatening problem or death caused by, or associated with, a device, if that effect, problem, or death was not previously identified in nature, severity, or degree of incidence in the investigational plan or application (including a supplementary plan or application), or any other unanticipated serious problem associated with a device that relates to the rights, safety, or welfare of subjects.

7.3 Adverse Event and Device Deficiency/Device Malfunction Reporting

7.3.1 Adverse Event Reporting

General AE Reporting

Safety surveillance and reporting starts as soon as the subject is registered in the clinical investigation. Safety surveillance and reporting will continue until the last follow-up visit has been performed, the subject is deceased, the subject concludes participation in the clinical investigation, or the subject withdraws from the clinical investigation. All adverse event data, including deaths and device deficiency data, will be collected throughout the time period defined above and will be reported to the Sponsor on a CRF. Additional information with regard to an adverse event should be updated within the appropriate CRF.

Unchanged, chronic, non-worsening or pre-existing conditions are not AEs and should not be reported. An offline form will be made available to allow the investigator to report AEs in the event the entry cannot be made in the electronic data capture (EDC) system. This does not replace the EDC reporting system. All information must still be entered in the EDC system as soon as feasible.

Clinical Investigation Plan

All cardiac related abnormal laboratory values should be reported as AEs.

Non-cardiac related abnormal laboratory values, in themselves, will not be considered AEs unless:

- The investigator determined that the value is clinically significant.
- The abnormal laboratory value required intervention, or
- The abnormal laboratory value required subject withdrawal from the clinical investigation.

All adverse events will be collected on each subject through the 2-year follow-up visit.

SAE Reporting

The investigator should report all SAEs to the Sponsor as soon as possible but no later than outlined below.

Clinical Site	Reporting timelines
All Sites	SAEs must be reported to the Sponsor no later than 3 calendar days from the day the site personnel became aware of the event or as per the investigative site's local requirements, if the requirement is more stringent than those outlined.

The date the site staff became aware the event met the criteria of an SAE must be recorded in the source document. The Investigator will further report the SAE to the local IRB/EC according to the institution's IRB/EC reporting requirements.

7.3.2 Unanticipated Serious Adverse Device Effect (USADE) Reporting to Sponsor and IRB

The Sponsor requires the Investigator to report any USADE to the Sponsor within 3 calendar days of the investigator's knowledge of the event, unless local requirements are more stringent, and to the IRB/EC per IRB/EC requirements.

7.3.3 Device Deficiency/Malfunction Reporting

All device deficiencies/malfunctions should be reported on the appropriate CRF form.

The investigator should report all device deficiencies/malfunctions to the Sponsor as soon as possible but no later than outlined below.

Clinical Sites	Reporting timelines
All Sites	Device deficiencies/malfunctions must be reported to the Sponsor no later than 3 calendar days from the day the site personnel became aware of the event or as per the investigative site's local requirements, if the requirement is more stringent than those outlined.

The device, if not implanted or not remaining in the subject, should be returned to the Sponsor.

Device deficiencies/malfunctions should be reported to the IRB/EC per the investigative site's local requirements.

Clinical Investigation Plan

An offline form will be made available to allow the investigator to report device deficiencies/malfunctions in the event that the entry cannot be made in the EDC system. This does not replace the EDC reporting system. All information must still be entered in the EDC system as soon as feasible.

7.3.4 Adverse Event Reporting to Country Regulatory Authorities by the Sponsor

The Sponsor will report SAEs and reportable device deficiencies/malfunctions to the country regulatory authority, per local requirements.

Note: Reportable device deficiencies/malfunctions include device deficiencies/malfunctions that might have led to an SAE if a) suitable action had not been taken or b) intervention had not been made or c) if circumstances had been less fortunate. These are handled under the SAE reporting system.

Clinical investigation SAEs and device deficiencies/malfunctions reportable per MedDEV 2.7/3 regulations will be submitted to European Competent Authorities by the Sponsor's Clinical Safety Group. Contact details are provided in [Appendix III].

8.0 STATISTICAL CONSIDERATIONS

The following section describes the statistical methods for the clinical investigation. [REDACTED]

8.1 Analysis Populations

The primary analysis of the primary endpoint will be based on the Full Analysis Set (FAS). All other descriptive analyses on the baseline characteristics and clinical endpoints will be performed on both the FAS population and the per-protocol (PP) population, except for that the acute success endpoint will be analyzed based on all registered population with the attempt of ABT NG DES 48 implantation.

[REDACTED]

[REDACTED]

[REDACTED]

[REDACTED]

[REDACTED]

Clinical Investigation Plan

8.2 Statistical Analyses

8.2.1 Primary Endpoint Analysis

The primary endpoint for this study is target lesion failure (TLF) at 1-year follow-up^c. The hypothesis against a pre-specified performance goal (PG) of 20% is:

$$H_0: \text{TLF} \geq 20\%$$
$$H_A: \text{TLF} < 20\%$$

8.2.2 Secondary Endpoint Analyses

Secondary endpoints will be summarized descriptively [REDACTED] For further details refer to the statistical analysis plan (SAP).

8.3 Sample Size Calculation and Assumptions

To test the hypothesis specified in Section 8.2.1 for the primary endpoint of TLF at 1-year follow-up, with the following assumptions:

- One-sided alpha: 0.05
- True event rate for the primary endpoint: 10%
- Performance goal: 20%
- Attrition rate: 5%

A sample size of 107 will have approximately 93% statistical power via simulation. To avoid undue influence from a single study site, each site may register at most 20% of the total subjects.

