2.2.2 Descriptive Statistics for Categorical Variables

[figure not shown]
For categorical variables such as cardiac death/Target-Vessel MI/CI-TLR or procedure and device success, results will be summarized with subject counts, percentages, and exact 95% Clopper-Pearson confidence intervals.

If warranted, comparison between subgroups intended for subgroup analysis will be conducted. Results within each comparison group will be summarized using the same statistics described as above for single group. Furthermore, differences between two comparison groups will be summarized with the difference in percentages and the asymptotic 95% confidence interval for the difference of two percentages.

[Redacted]

[Redacted]

[Redacted]

Statistical Analysis Plan**2.2.3 Survival Analyses**

Survival analysis will be conducted to analyze time-to-event variables^[5]. Survival curves will be constructed using Kaplan-Meier estimates for analyzing the survival distributions through 30 days, 180 days, 1 and 2 years for clinical endpoints. Subjects without events will be censored at their last known event-free time point.

2.2.4

[Redacted]

[Redacted]

[Redacted]

Statistical Analysis Plan

[REDACTED]

[REDACTED]

[REDACTED]

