2.3 Endpoint Analysis

Statistical testing of the primary endpoint will be one-tailed and performed at the 0.05 significance level against a pre-specified performance goal. Analyses of other trial endpoints will be descriptive in nature. The clinical endpoints will be determined per protocol.

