2.3.1 Primary Endpoint

The primary endpoint for this study is target lesion failure (TLF), defined as a composite of cardiac death, target vessel myocardial infarction [TV-MI] (MI is per Society for Cardiovascular Angiography and Interventions (SCAI) definition^[1]), and clinically indicated target lesion revascularization [CI-TLR] at 1 year. The 1-year TLF will be compared to a pre-specified performance goal of 20%.

The null (H_0) and alternative (H_A) hypotheses are stated as:

$$H_0: P_D \geq 20\%$$

$$H_A: P_D < 20\%$$

Where P_D represents the target lesion failure (TLF) rate at 1 year. The primary endpoint will be performed on the FAS population.

[REDACTED] The primary endpoint will be considered met if the null hypothesis is rejected at the one-sided 5% significance level.

Descriptive summary of TLF at different follow-ups may be displayed for the FAS and PP population.

[REDACTED]

Statistical Analysis Plan

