2.4 Sample Size Calculations

To test the hypothesis specified for the primary endpoint of TLF at 1-year follow-up, with the following assumptions:

- One-sided alpha: 0.05
- True event rate for the primary endpoint: 10%
- Performance goal: 20%
- Attrition rate: 5%

[REDACTED]

A total sample size of 107 will provide approximately 93% power to test the primary endpoint [REDACTED]

[REDACTED] To avoid undue influence from a single study site, each site may register at most 20% of the total subjects.

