2.13 Sensitivity Analysis

The following sensitivity analyses of the primary endpoint will be carried out:

- The primary endpoint will be performed for the per-protocol (PP) population as a sensitivity analysis.
- Tipping point analysis will be conducted as a sensitivity analysis to evaluate the impact of the missing data for the primary endpoint.

[REDACTED]

[REDACTED]

Statistical Analysis Plan

- COVID-19 Related Events: [REDACTED]
- The exact test based on the binomial distribution will be conducted to test the primary endpoint [REDACTED]

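### The stated 93% power is out of reach for any one-sided 5% binomial test with 107 subjects; a test that holds 5% gives about 86–87%, and the tests that do give 93% have a real type I error of about 7–8%.

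*Protocol*

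**What the plan says.** Protocol 8.3 sets "One-sided alpha: 0.05", a true event rate of 10%, a goal of 20% and 5% attrition, and concludes: "A sample size of 107 will have approximately 93% statistical power via simulation". SAP 2.4 repeats the inputs and the result: "A total sample size of 107 will provide approximately 93% power to test the primary endpoint".

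The 5% level is also the decision level. SAP 2.3: "Statistical testing of the primary endpoint will be one-tailed and performed at the 0.05 significance level against a pre-specified performance goal". SAP 2.3.1: "The primary endpoint will be considered met if the null hypothesis is rejected at the one-sided 5% significance level".

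The primary test statistic and the simulation details are redacted. Two visible passages bear on them. SAP 2.13 puts the exact test among the sensitivity analyses: "The exact test based on the binomial distribution will be conducted to test the primary endpoint". SAP 2.2.3 names Kaplan-Meier for time-to-event endpoints. For categorical results such as TLF, SAP 2.2.2 says "results will be summarized with subject counts, percentages, and exact 95% Clopper-Pearson confidence intervals".

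**The concern.** At this sample size a 10% versus 20% comparison at one-sided 5% should have power in the upper 80s, so 93% suggests a rule more lenient than its label. The exact test appears only as a sensitivity analysis, so the primary test is presumably a large-sample one. Such tests can exceed their nominal level when the variance is estimated from few events: a low event count also gives a small standard error.

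This is the only formal test in a single-arm IDE trial meant to support US approval. If the rule really runs at 7–8%, a device that only just fails the goal passes more often than the plan says. There is also a foreseeable result, 14 events, at which the primary analysis would declare success and the sponsor's own exact analysis would not.

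**Working it through.** **Inputs** (Protocol 8.3, SAP 2.4): p0 = 0.20, p1 = 0.10, one-sided alpha 0.05, N = 107, attrition 5%. Evaluable: 107 × 0.95 = 101.65, so 101 or 102. X is the number of subjects with TLF by 1 year.

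**1. Reproducing 93%.** The Wald test rejects when (X/n − 0.20) / √[(X/n)(1 − X/n)/n] < −1.645. At n = 101, X = 14: (0.1386 − 0.20)/0.0344 = −1.79, rejected. X = 15: (0.1485 − 0.20)/0.0354 = −1.46, not rejected. The cut-off is therefore 14. Power is P(X ≤ c | 0.10); true size is P(X ≤ c | 0.20).

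| Estimated-variance test | Cut-off c | Power | True size |
|---|---|---|---|
| Wald, n = 101 | 14 | 92.2% | 7.4% |
| Wald, n = 102 | 14 | 91.7% | 6.75% |
| Wald, n = 107 | 15 | 93.3% | 7.3% |
| KM, Greenwood, plain scale | – | 92.6–93.6% | 7.2–7.8% |
| KM, Greenwood, log-survival scale | – | 93.6–93.9% | 7.7–8.3% |

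The KM rows are simulations (60,000 trials, 107 subjects, 5% exponential dropout, with constant hazard or with 30–70% of events at the procedure). The event-time patterns are assumptions; the documents give none.

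**2. The exact test.** Take the largest c with P(X ≤ c | n, 0.20) ≤ 0.05.

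| n | c | Size | Power |
|---|---|---|---|
| 101 | 13 | 4.26% | 86.9% |
| 102 | 13 | 3.86% | 86.1% |
| 107 (no loss) | 14 | 4.27% | 88.7% |

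The score and mid-p tests have the same cut-offs at these n. Averaged over Binomial(107, 0.95) evaluable subjects, exact power is 85.3%. KM with complementary log-log limits, in the same simulations, has 87.4–89.0% power and 4.1–4.5% size.

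**3. Upper bound for any 5% test of 1-year TLF status.** By the Neyman-Pearson lemma the most powerful test rejects at X ≤ c and, at X = c + 1, rejects with probability g = (0.05 − size)/P(X = c + 1 | 0.20). At n = 107: g = (0.0427 to 0.05 gap)/0.0300 = 0.24, and power = 0.8866 + 0.24 × 0.0465 = 0.898. At n = 101 and 102 the bound is 88.1% and 88.3%. Using event times does not help much: the most powerful constant-hazard test, with all 107 followed for a year, reaches about 90% in simulation.

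**4. N needed for 93%.** The exact test first reaches 93% at 124 evaluable subjects and stays above it from 135.

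**5. Where the rules disagree.** At 14 events of 101 or 102, Wald declares success; the exact p-value is 0.074 or 0.068. The one-sided 95% exact upper bound is 20.8% or 20.6%, above the goal. The two-sided 95% Clopper-Pearson upper limit is about 22%.

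**The case against.** The best defence is that 93% is not a miscalculation. It is about what a simulation of a nominal-5% Kaplan-Meier/Greenwood or Wald test returns, and nothing visible says the primary test is binomial. That is right, and it means the defect may lie in the level rather than in the power. It does not remove the defect, because the plan states the 5% level without qualification in four places and such a test does not hold it at this N.

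The redactions also matter. The test statistic, the success criterion and the simulation model are hidden, and hidden text may already report the actual type I error. So the choice of primary test is an inference; the bound in step 3 is not.

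The practical gap is one event. Exactly 14 events at n = 101–102 has probability 5.4–5.6% if the true rate is 10% and 2.9–3.1% if it is 20%, and the planned exact test would expose the disagreement. This limits the harm, but that one event is the difference between the stated error rate and the real one.

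The 22% limit is not a fair yardstick for a one-sided 5% test; the matching bound is 20.6–20.8%, which still misses the goal.

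Finally, log-log limits are not exact: with complete data their size is 5.16% at n = 99 and 5.14% at n = 105. That excess is trivial beside 7–8%, but only the exact test guarantees 5%.

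**Conclusion.** The concern holds. The stated inputs and 93% power are incompatible: no 5% test of 1-year TLF status exceeds 89.8% power even with no attrition. A valid test gives 86–87% at 101–102 evaluable subjects, or 85.3% for the exact test averaged over random attrition. If 93% is the real power, the real type I error is about 7–8%, or 1.4–1.6 times nominal (7.1/5 to 8.0/5).

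The bound rests only on the published inputs and independent subjects. That the simulated test was a Wald-type or Kaplan-Meier/Greenwood test is inferred from the match to 93% and from the exact test's place among the sensitivity analyses. Power stays above 85% under a valid rule, so the trial is adequately sized; the rule and its description need correcting.

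**What to change.** - Make the primary rule one that holds 5%: the exact binomial test, or the one-sided 95% upper bound of the Kaplan-Meier 1-year TLF rate on the complementary log-log scale falling below 20%. Keep any Wald or Greenwood z test as a sensitivity analysis.
- In Protocol 8.3 and SAP 2.4, name the test and restate power from a re-run simulation: about 87% for Kaplan-Meier with log-log limits, 85–87% for the exact test. Give the simulated type I error at a true rate of 20% beside it.
- Report the primary result with the one-sided 95% upper bound (the upper limit of a two-sided 90% interval), so that interval and test agree.
- If the large-sample test stays primary, state its actual type I error rather than 5%.

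The rule must be fixed before 1-year outcomes are seen, because one event separates the candidates. The cost is protocol and SAP wording plus a simulation re-run. N stays at 107; the stated power falls from 93% to about 87%.
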